9.3.13 Follow-Up OL Visit (28 \pm 3 days Post OL End of Dosing)

- Physical examination (symptom-directed)
- Vital signs ([Section 9.2.6](#))
- Laboratory assessments including thyroid functions ([Section 9.2.8](#))
- Serum β -hCG pregnancy test ([Section 9.2.8](#)) if indicated
- ECG ([Section 9.2.10](#))
- AFP
- Hepatitis B and/or C viral load (for subjects with measurable viral load at the Baseline Visit)
- Concomitant medications
- Adverse events

10.0 EFFICACY AND PHARMACOKINETICS ASSESSMENTS

10.1 Response Assessments

Data on primary disease, response, and the duration of any OR or SD, as well as the TTP, PFS, and OS will be collected for all subjects. Subjects will undergo disease assessment at Pre-Study (within 28 days prior to first dose of study drug), at the end of Cycle 2, and at the end of even-numbered cycles thereafter. Response will be determined by RECIST version 1.1 as modified by [Santoro \(2013\)](#) ([Appendix A](#)).

Disease parameters to be assessed:

- Diagnostic imaging/measurement of target lesions
- Response assessment

10.1.1 Disease Classification

Details of the primary diagnosis should be documented at the Pre-Study Visit. The histological/cytological type (if known) and stage of disease should be noted on the CRF.

10.1.2 Diagnostic Imaging/Measurement of Target Lesions

Subjects should be followed with the same imaging procedure (CT scan or MRI) throughout this trial. If PD is documented at any time, no further imaging or lesion measurements will be required. Diagnostic studies documenting response must be available for Sponsor review.

10.1.3 Response Assessment

Response will be assessed as detailed in Appendix A. Efficacy will be assessed for the Intent-to-Treat (ITT) Population ([Section 12.3.2](#)).

10.2 Time to Event

The time to event assessments include OS, TTP, and PFS. Overall Survival (OS) is the number of days from Day 1 of Cycle 1 to the day of death+1, where a death can be due to any cause. Subjects who discontinue will be followed indefinitely to obtain survival status. Time to Progression (TTP) is the number of days from Day 1 of Cycle 1 to the day of PD+1. Progression-Free Survival is the number of days from Day 1 of Cycle 1 to the day of death or PD+1.

10.3 Laboratory Assessments for Exploratory Efficacy

Certain laboratory parameters associated with hepatic dysfunction and cirrhosis will be examined, as will WBC A₃AR expression.

10.3.1 Liver Chemistry Tests

Bilirubin (direct and total), ALT, AST, and albumin will be performed along with other laboratory tests assessed for safety at Pre-Study Visit; Days 1 (i.e., the Baseline Visit if not performed within 3 days prior), 8, and 15 of Cycle 1; Days 1 and 15 of subsequent cycles; EOS; and Follow-up/Days 1, 8, and 15 of OL Cycle 1; Days 1 and 15 of subsequent OL cycles; OL EOS; and OL Follow-up.

10.3.2 INR

INR will be assessed along with other laboratory tests assessed for safety at the Pre-Study Visit; Days 1 (i.e., the Baseline Visit if not performed within 3 days prior), 8, and 15 of Cycle 1; Days 1 and 15 of subsequent cycles; EOS; and Follow-up/ Days 1, 8, and 15 of OL Cycle 1; Days 1 and 15 of subsequent OL cycles; OL EOS; and OL Follow-up.

10.3.3 Viral Load

For subjects with measurable viral load at the Baseline Visit, hepatitis B and/or C viral load will be measured on Day 1 of odd-numbered cycles/ Day 1 of OL odd-numbered cycles only.

10.4 Pharmacokinetics Assessment

All subjects enrolled at sites with the requisite technical capabilities will have approximately 8 whole blood samples collected during Cycle 1 and 2 for analysis of plasma concentrations of CF102. Approximately 4 mL of blood will be collected from subjects at each time point (i.e., a total of approximately 32 mL).

The timing of PK sampling is shown in Table 10-1. Sparse PK samples will be collected following the morning dose of CF102 on Cycle 1 Day 1 and Cycle 2 Day 1. In addition, a trough sample will be collected pre-AM dose on Cycle 1 Days 8 and 15. If PK samples are to be drawn at a scheduled safety evaluation visit, the study drug should be held until after the pre-dose PK sample has been drawn and safety assessments have been performed.

Table 10–1: Timing of PK Samples

Timing Relative to Time of AM Dose (T)	Cycle 1			Cycle 2
	Day 1	Day 8	Day 15	Day 1
Pre-dose (AM dose)	X	X	X	X
Post-dose 1, 2, 3, 4, 6, 8, and 12h (prior to the evening dose) ^a	X			X

a. On Day 1 of Cycles 1 and 2, after the morning dose, PK blood samples will be collected at ANY TWO of the specified time points (1, 2, 3, 4, 6, 8, and 12h [prior to evening dose])

Plasma CF102 concentration will be determined using a validated LC-MS/MS method by a Sponsor-designated laboratory.

10.4.1 Sample Storage

Plasma samples will be placed in a storage freezer at -70°C (± 12°C) or on dry ice within 120 minutes of the blood collection. Samples should be placed in a -70°C (± 12°C) freezer until they

are shipped to the bioanalytical laboratory. With prior approval from the Sponsor, sample storage in a -20°C freezer may be permitted.

The complete procedure is detailed in the laboratory manual provided by the central laboratory.

11.0 ASSESSMENT OF SAFETY

11.1 Safety Parameters

Safety parameters assessed throughout the trial include ECOG performance status; vital signs; weight; physical examinations; laboratory parameters; ECG; concomitant medications, and adverse events. Any clinically significant change from baseline in a laboratory parameter will be reported as an AE. Liver Chemistry Tests, INR, and viral load will be presented as exploratory efficacy variables, as will WBC A₃AR expression.

Anticipated toxicities that may occur with CF102 are detailed in [Section 4.4](#) of this protocol as well as in the Investigator Brochure (IB).

11.2 Duration of Follow-Up

Any significant clinical adverse event, whether observed by the Investigator or experienced by the subject, will be reported beginning with the Cycle 1 Day 1 (Baseline) Visit. Final safety evaluations will be performed at the 28-day Follow-Up Visit (28 ± 3 days post End of Dosing)/OL Follow-Up Visit (28 ± 3 days post OL End of Dosing). If the subject begins an alternative treatment, then the Follow-Up visit will be performed as soon as possible. Every effort will be made to obtain and record survival information for each subject, who will be followed indefinitely for survival with, for example, monthly telephone calls.

If an observed toxicity thought to be at least possibly related to study drug has not resolved by the 28-Day Follow-Up Visit/OL Follow-Up Visit, the subject will continue to be followed until the event has resolved or stabilized.

11.3 Safety Data Review During the Trial

The Medical Monitor will review safety data on an ongoing basis throughout the trial.

- All serious adverse events (SAEs) must be reported to the Sponsor within 24 hours of the Investigator becoming aware of the SAE ([Section 11.5](#)).
- Adverse events resulting in a subject's permanent discontinuation from the trial, regardless of seriousness or relationship to study drug, must be promptly reported to the Sponsor.
- The AE pages of each subject's CRF must be completed and submitted to the Sponsor or designee within 2 weeks of each visit.

Availability of these data will also enable the Sponsor to notify other participating trial centers and regulatory authorities of events occurring during the trial.

Safety decisions will be documented and communicated in writing to sites.

11.4 Adverse Event Definitions/Reporting Requirements

11.4.1 Adverse Event

An AE (also known as an “adverse experience”) is defined as any untoward medical occurrence associated with the use of a drug in humans, whether or not considered drug related (CFR 312.32).

An AE can therefore be any unfavorable and unintended sign (including an abnormal laboratory finding), symptom, or disease temporally associated with the use of the drug, without any judgment about causality.

All clinical AEs noted during the trial will be reported on the appropriate AE page of the CRF (paper or electronic).

11.4.2 Suspected Adverse Reaction

A suspected adverse reaction is a subset of all AEs for which there is a reasonable possibility (i.e., evidence to suggest a causal relationship between the drug and the AE) that the drug caused the event. Suspected adverse reaction implies a lesser degree of certainty about causality than adverse reaction. Document suspected adverse reactions on the AE page of the CRF.

11.4.3 Adverse Reaction

An adverse reaction is a subset of all suspected adverse reactions, and is defined as any AE caused by a drug. Document any adverse reactions on the AE page of the CRF.

11.4.4 Unexpected Adverse Event/Unexpected Suspected Adverse Reaction

An unexpected AE (or unexpected suspected adverse reaction) is any AE or suspected adverse reaction that is not listed in the IB or is not listed at the specificity or severity that has been observed, if an IB is not required/available, is not consistent with the risk information described in the general investigational plan. This also refers to AEs or suspected adverse reactions mentioned in the IB as occurring with a class of drugs or as anticipated from the pharmacological properties of the drug, but are not specifically mentioned as occurring with the study drug.

The Sponsor should be notified within 24 hours of the Investigator becoming aware of the event. Document unexpected AEs on the AE page of the CRF.

11.5 Serious Adverse Event Definitions/Reporting Requirements

11.5.1 Serious Adverse Event or Serious Suspected Adverse Reaction

An AE or suspected adverse reaction is considered serious if, in the view of either the Investigator or Sponsor, it results in any of the following outcomes:

1. Death. This includes any death that occurs while the subject is enrolled in the trial and/or within 30 days after the last dose of study drug. An autopsy will be requested, and if performed, results will be submitted to the Sponsor.
2. A life-threatening adverse event. An AE or suspected adverse reaction is considered life-threatening if, in the view of either the Investigator or Sponsor, its occurrence places the subject at immediate risk of death. It does not include a reaction that had it occurred in a more severe form, might have caused death.
3. Inpatient hospitalization or prolongation of existing hospitalization. In the absence of an AE, hospitalization or prolongation of hospitalization should not be reported as an SAE in the following situations:
 - Hospitalization or prolongation of hospitalization is needed for a procedure required by the protocol.
 - Hospitalization or prolongation of hospitalization is part of routine procedure followed by trial center.
 - Hospitalization for survey visits or annual physicals.
 - For a hospitalization planned (and documented) before the start of the trial for a pre-existing condition which has not worsened.
4. A persistent or significant incapacity or substantial disruption of the ability to conduct normal life functions.
5. A congenital anomaly/birth defect.
6. Important medical events that may not result in death, be life-threatening, or require hospitalization may be considered serious when, based upon appropriate medical judgment, they may jeopardize the subject and may require medical or surgical intervention to prevent one of the outcomes listed in this definition. Examples include allergic bronchospasm requiring intensive treatment in an emergency room or at home, blood dyscrasias or convulsions that do not result in inpatient hospitalization, or the development of drug dependency or drug abuse.

The Sponsor should be notified within 24 hours of the Investigator becoming aware of the event. Document SAEs on the AE/SAE page(s) of the CRF.

11.5.1.1 Pregnancy

For safety reporting purposes, any pregnancy occurring during the trial will be considered an “important medical event” (Section 11.5.1). It is not known whether study drug can cause fetal harm when administered to a pregnant woman or whether it can affect reproductive capacity. There have been no studies in pregnant women. Study drug should only be administered to women of childbearing potential when appropriate contraceptive measures have been taken and when pregnancy tests are negative. A negative serum β -hCG pregnancy test must be documented on the CRF prior to the first dose of study drug and periodically throughout the trial.

Studies have not been performed to determine whether CF102 affects reproductive function in males. Men and women with childbearing potential will be informed as to the unknown risks to a pregnancy and will be advised that they must both use effective contraception during the trial and for 3 months afterward. Effective birth control includes (a) IUD plus one barrier method, or (b) 2 barrier methods. Effective barrier methods are male or female condoms, diaphragms, and spermicides.

If a trial subject becomes pregnant while participating in the trial, the study drug will be discontinued immediately and the pregnancy will be reported to the Sponsor. The Investigator will then report follow-up information to the Sponsor regarding the course of the pregnancy, including perinatal and neonatal outcome, regardless of the fact that the subject has discontinued the trial. Once the newborn is determined to be healthy, as defined by and agreed upon by the Sponsor and Investigator, additional follow-up will no longer be required.

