7.2 Exclusion Criteria

Subjects meeting any of the following criteria are ineligible for the trial:

1. Receipt of no, or of > 1 , prior systemic drug therapies for HCC.
2. Receipt of systemic cancer therapy, immunomodulatory drug therapy, immunosuppressive therapy, or corticosteroids > 20 mg/day prednisone or equivalent within 14 days prior to the Baseline Visit or concurrently during the trial.
3. Presence of an acute or chronic toxicity of prior chemotherapy that has not resolved to \leq Grade 1, as determined by CTCAE v 4.0.
4. Locoregional treatment within 4 weeks prior to the Baseline Visit.
5. Major surgery or radiation therapy within 4 weeks prior to the Baseline Visit.
6. Use of any investigational agent within 4 weeks prior to the Baseline Visit.
7. Child-Pugh Class A or C cirrhosis, or hepatic encephalopathy.
8. Occurrence of esophageal or other gastrointestinal hemorrhage requiring transfusion within 4 weeks prior to the Baseline Visit.
9. Uncontrolled or clinically unstable thyroid disease, per judgment of the Principal Investigator.
10. Active bacterial, viral, or fungal infection requiring systemic therapy, or operative or radiological intervention.

11. Known human immunodeficiency virus- or acquired immunodeficiency syndrome-related illness.
12. Liver transplant.
13. Active malignancy other than HCC.
14. Uncontrolled arterial hypertension or congestive heart failure (New York Heart Association Classification 3 or 4) ([Appendix B](#)).
15. Angina, myocardial infarction, cerebrovascular accident, coronary/peripheral artery bypass graft surgery, transient ischemic attack, or pulmonary embolism within 3 months prior to initiation of study drug.
16. History of or ongoing cardiac dysrhythmias requiring treatment, atrial fibrillation of any grade, or persistent prolongation of the QTc (Fridericia) interval to > 450 msec for males or > 470 msec for females.
17. Pregnant or lactating female.
18. Women of childbearing potential, unless they agree to use dual contraceptive methods which, in the Investigator's opinion, are effective and adequate for the subject's circumstances while on study drug.
19. Men who partner with a woman of childbearing potential, unless they agree to use effective, dual contraceptive methods (i.e., a condom, with female partner using oral, injectable, or barrier method) while on study drug and for 3 months afterward.

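### Exclusion Criterion 18 asks women to agree to contraception during treatment only, while Protocol 11.5.1.1 adds 3 months, so a woman can be eligible without committing to the post-treatment period

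*Protocol*

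**What the plan says.** **Women, at entry.** Criterion 18 in Protocol 7.2 excludes "Women of childbearing potential, unless they agree to use dual contraceptive methods which", in the Investigator's view, "are effective and adequate for the subject's circumstances while on study drug". The duration is the same in the synopsis, in SAP 4.2 and in the criteria text attached to mock Listing 16.2.2.2. No list of methods is given.

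**Men, at entry.** Criterion 19 requires men with a partner of childbearing potential to agree to "dual contraceptive methods (i.e., a condom, with female partner using oral, injectable, or barrier method) while on study drug and for 3 months afterward".

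**Both sexes, during conduct.** Protocol 11.5.1.1 states that the effect on a fetus is not known and that pregnant women have not been studied. It says that men and women will be informed of the unknown risk and advised that "they must both use effective contraception during the trial and for 3 months afterward". On methods it says "Effective birth control includes (a) IUD plus one barrier method, or (b) 2 barrier methods", and it gives condoms, diaphragms and spermicides as the barrier methods.

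**Open label.** Protocol 7.7 sets two conditions: a signed open-label consent, and still taking blinded medication when Amendment 5 is approved. Contraception is not mentioned. Section 8.0 ties open-label dosing to 7.7, whereas blinded dosing is tied to 7.1 and 7.2.

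**The concern.** Two parts of the same protocol state different contraception periods for women. The eligibility criterion, to which each woman's agreement is recorded at entry, stops at the end of treatment. The safety section runs 3 months longer. The gap is conspicuous because Criterion 19, directly below, does state the 3 months for men.

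What is at stake is the protection of participants, not the estimate of effect. The protocol itself says that the risk to a pregnancy is unknown. The last scheduled clinic visit is the Follow-Up Visit, 28 ± 3 days after the End of Dosing visit; after that, only survival contact is described. For most of a 3-month period, then, the safeguard is what the woman was told and what she agreed to, and that is where the texts differ.

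**Working it through.** There is no planned figure to reproduce, since the point involves no sample size, event count or error rate. The check is a comparison of texts.

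| Item | Criteria 18 and 19 | Protocol 11.5.1.1 | Result |
|---|---|---|---|
| Women: period after treatment | None stated (18) | 3 months | Differ |
| Men: period after treatment | 3 months (19) | 3 months | Agree |
| Start of the 3 months | End of study drug (19) | End of the trial, as worded | Differ |
| Women: methods | Dual, Investigator's judgement, no list (18) | IUD plus barrier, or two barriers, introduced by a verb that need not be exhaustive | No direct conflict |
| Men and partners: methods | Condom plus partner's oral, injectable or barrier method (19) | As above; oral and injectable not named | Unclear for oral and injectable |

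**Step 1, duration for women.** Suppose a woman agrees to dual contraception until her last dose and no further. Criterion 18 is met in every copy. The 3 months in 11.5.1.1 form no part of what she agreed to. Eligibility therefore does not secure the commitment that 11.5.1.1 describes.

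**Step 2, start point.** Section 11.5.1.1 counts from the end of the trial, and Criterion 19 from the end of study drug. Protocol 6.1 and 7.4 have subjects who discontinue followed indefinitely for survival. For such a subject the end of the trial has no fixed date, so the start of the 3 months in 11.5.1.1 is undefined. This affects men as well as women.

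**Step 3, how much of the period lies beyond scheduled visits.** Assume that the 3 months run from the End of Dosing visit and that a month is 30 days, the conversion SAP 7.6.1 uses for survival time. Then 3 × 30 = 90 days, and 90 − 28 = 62 days fall after the Follow-Up Visit. With the ± 3 day window the range is 90 − 31 = 59 to 90 − 25 = 65 days. About two of the three months have no scheduled clinic visit.

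**Step 4, methods.** Criterion 19's condom plus a partner's barrier method matches option (b) of 11.5.1.1. What remains is that oral and injectable methods are named in one place and not in the other.

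**Step 5, open label.** Section 7.7 does not re-apply Criteria 18 and 19, and the synopsis places those criteria under the double-blind portion. Section 11.5.1.1 is therefore the protocol's general contraception text for subjects on open-label dosing.

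**The case against.** The strongest reply is that both texts can be followed at once. Criterion 18 is a test at entry and 11.5.1.1 is an instruction for conduct; a woman who uses contraception for the longer period satisfies both. Criterion 18 omits the 3 months but does not say that she may stop. This stands in part. A reader might infer that sites would let women stop at the last dose, or that an eligible woman is in breach of the protocol. Neither follows: both inferences assume that the site disregards 11.5.1.1. What is left is that the recorded agreement is shorter than the period advised.

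A reader might also infer that the accepted methods contradict each other for both sexes. The documents do not support that. The verb that introduces the options in 11.5.1.1 can be read as non-exhaustive, and Criterion 18 contains no list that could conflict. This part is an ambiguity about oral and injectable methods.

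It might further be inferred that indefinite open-label dosing keeps the conflict with Criterion 18 live for new entries. Open-label entry does not apply that criterion, and Protocol 4.4 says the only patients still on treatment at Amendment 5 are in Romania. Rewording the criteria now would change no enrolment decision. The open-label point is narrower: 7.7 is silent, so the rule rests on 11.5.1.1, whose start point is undefined.

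Two more replies have weight. The schedules of events include serum pregnancy tests each cycle, at End of Dosing and at Follow-Up (the visit lists in 9.3 add that they are done if indicated), and a pregnancy leads to discontinuation and follow-up under 11.5.1.1. These cover treatment and roughly the first month after it. The consent forms are not among the documents reviewed and may already state the 3 months for women.

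**Conclusion.** The inconsistency is real but limited. For women, Criterion 18 states no post-treatment contraception period and 11.5.1.1 states 3 months, so eligibility can be met without a commitment to those months. Two lesser points go with it: the start of the 3 months is undefined in 11.5.1.1, and the status of oral and injectable methods is unclear.

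The conclusion rests on the protocol and SAP text alone. It does not assume that any site or participant acted on the shorter period, and it takes no position on which duration or method list is right. The number of women of childbearing potential is not given and may be small. There is no effect on data, power or analysis.

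**What to change.** Reconcile Criteria 18 and 19 (synopsis, Protocol 7.2, and the copies in SAP 4.2 and the mock listing) with Protocol 11.5.1.1, so that for each sex there is:

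- one contraception period, with a defined start point;
- one description of acceptable methods, saying whether the list is exhaustive and where oral and injectable methods stand.

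Make sure the open-label provisions state the same rule, either in 7.7 or by explicit reference to 11.5.1.1, and check that the open-label consent agrees with it. The sponsor's medical team must decide which rule applies.

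The cost is wording in the next amendment and, if the check shows a difference, in the open-label consent. No data collection, analysis or table changes.

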11.5.2 Serious and Unexpected Suspected Adverse Reaction

A serious and unexpected suspected adverse reaction (SUSAR) is any SAE related to study drug, the specificity or severity of which is not consistent with those noted in the current protocol and/or IB. This also refers to adverse events or suspected adverse reactions mentioned in the IB as occurring with a class of drugs or as anticipated from the pharmacological properties of the drug, but are not specifically mentioned as occurring with the study drug.

The Sponsor should be notified within 24 hours of the Investigator becoming aware of the event. Document SUSARs on the AE/SAE page(s) of the CRF.

